10.4. Other Response Parameters

10.4.1. Molecular response: measured by change in blood (and/or marrow) allelic ratio of MPN driver mutations (JAK2, CALR or MPL).

10.4.2 Histologic response: measured by change in bone marrow biopsy cellularity and fibrosis grade.

10.4.3 SMAD2/3 phosphorylation: Measured in peripheral blood and/or bone marrow hematopoietic cells.

11. Data Reporting / Regulatory Considerations

11.1 Data Collection

The data collection plan for this study is to utilize REDCap to capture all treatment, toxicity, efficacy, and adverse event data for all enrolled subjects.

11.1.1 REDCap

REDCap (Research Electronic Data Capture) is a free data management software system that is fully supported by the Weill-Cornell Medical Center CTSC. It is a tool for the creation of customized, secure data management systems that include Web-based data-entry forms, reporting tools, and a full array of security features including user and group based privileges, authentication using institution LDAP system, with a full audit trail of data manipulation and export procedures. REDCap is maintained on CTSC-owned servers that are backed up nightly and support encrypted (SSL-based) connections. Nationally, the software is developed, enhanced and supported through a multi-institutional consortium led by the Vanderbilt University CTSA.

11.2 Regulatory Considerations

11.2.1 Institutional Review Board/Ethics Committee Approval

As required by local regulations, the Investigator will ensure all legal aspects are covered, and approval of the appropriate regulatory bodies obtained, before study initiation.

Before initiation of the study at each study center, the protocol, the ICF, other written material given to the patients, and any other relevant study documentation will be submitted to the appropriate Ethics Committee. Written approval of the study and all relevant study information must be obtained before the study center can be initiated or the IP is released to the Investigator. Any necessary extensions or renewals of IEC/IRB approval must be obtained for changes to the study, such as amendments to the protocol, the ICF, or other study documentation. The written approval of the IEC/IRB together with the approved ICF must be filed in the study files.

The Investigator will report promptly to the IEC/IRB any new information that may adversely affect the safety of the patients or the conduct of the study. The Investigator will submit written summaries of the study status to the IEC/IRB as required. On completion of the study, the IEC/IRB will be notified that the study has ended.

Neither the Investigator nor MedPacto will modify or alter this protocol without the agreement of the other. All agreed protocol amendments will be clearly recorded on a protocol amendment form and will be signed and dated by the original protocol approving signatories. All protocol

amendments will be submitted to the relevant institutional IEC/IRB for approval before implementation, as required by local regulations. The only exception will be when the amendment is necessary to eliminate an immediate hazard to the trial participants. In this case, the necessary action will be taken first, with the relevant protocol amendment following shortly thereafter.

Once protocol amendments or consent form modifications are implemented at the lead site, Weill Cornell Medicine, updated documents will be provided to participating sites. Weill Cornell Medicine must approve all consent form changes prior to local IRB submission.

Relevant study documentation will be submitted to the regulatory authorities of the participating countries, according to local/national requirements, for review and approval before the beginning of the study. On completion of the study, the regulatory authorities will be notified that the study has ended.

11.2.2 Ethical Conduct of the Study

The Investigators and all parties involved should conduct this study in adherence to the ethical principles based on the Declaration of Helsinki, GCP, ICH guidelines and the applicable national and local laws and regulatory requirements.

This study will be conducted under a protocol reviewed and approved by the applicable ethics committees and investigations will be undertaken by scientifically and medically qualified persons, where the benefits of the study are in proportion to the risks.

11.2.3 Informed Consent

The investigator or qualified designee must obtain documented consent according to ICH-GCP and local regulations, as applicable, from each potential subject or each subject's legally authorized representative prior to participating in the research study. Subjects who agree to participate will sign the approved informed consent form and will be provided a copy of the signed document.

The initial ICF, any subsequent revised written ICF and any written information provided to the subject must be approved by IRB prior to use. The ICF will adhere to IRB/IEC requirements, applicable laws and regulations.

11.2.4 Compliance with Trial Registration and Results Posting Requirements

Under the terms of the Food and Drug Administration Modernization Act (FDAMA) and the Food and Drug Administration Amendments Act (FDAAA), the Sponsor-Investigator of the trial is solely responsible for determining whether the trial and its results are subject to the requirements for submission to <http://www.clinicaltrials.gov>. Information posted will allow subjects to identify potentially appropriate trials for their disease conditions and pursue participation by calling a central contact number for further information on appropriate trial locations and trial site contact information.

11.2.5 Record Retention

Essential documents are those documents that individually and collectively permit evaluation of the study and quality of the data produced. After completion of the study, all documents and data relating to the study will be kept in an orderly manner by the Investigator in a secure study file. Essential documents should be retained for 2 years after the final marketing approval in an ICH region or for at least 2 years since the discontinuation of clinical development of the IP. In addition, all subjects' medical records and other source documentation will be kept for the maximum time permitted by the hospital, institution, or medical practice.

12. Statistical Considerations

12.1 Study Design/Endpoints

12.1.1. Optimal Two-Stage Design, and Criteria to Proceed to Tier 2:

A Simon Two-stage Optimum Design was used to minimize the number of subjects exposed to vactosertib if it is found to be an unsuitable agent for the treatment of anemic patients with Ph-neg MPNs. Further development of vactosertib would be warranted if $\geq 20\%$ of subjects met *Criteria for Clinical Benefit* ([section 10.1](#)) without dose-limiting toxicity (see *Definition of Dose Limiting Toxicity* section). The study will be terminated early if fewer than 1 subject treated in the first tier (up to 12 subjects) meet these criteria. Using these criteria, there is less than a 10% chance of inappropriately accepting (α , type 1 error) vactosertib if it is not truly useful. Conversely, there is less than a 10% chance of inappropriately rejecting (β , type 2 error) vactosertib if it is actually a useful drug for anemic patients with Ph-neg MPNs.

Table 4: Optimal Two Stage Design

Response Probability Indicating Unacceptably Low vactosertib Activity	0.05
Response Probability Indicating Substantial vactosertib Activity	0.20
Probability of Accepting Poor Drug	0.1
Probability of Rejecting Good Drug	0.1
Number of Tier 1 Subjects	12
Number of Tier 1 Responders to Advance to Tier 2	≥ 1
Maximal Number of Subjects	37
Number of Tier 2 Responders to Advance Development	≥ 4

The Simon Two-stage Optimum Design is expected to minimize the number of subjects exposed to vactosertib if it is found to be an unsuitable agent for the treatment of anemic patients with Ph-neg MPNs (see *Criteria for Decision to Proceed to Tier 2* section). If 1 or more subjects meets the *Composite Response & Toxicity Endpoint* ([Table 5](#)) then the study will proceed to Tier 2 and another 25 subjects will be enrolled. After completion of Tier 2, if four or more subjects meet the *Composite Response & Toxicity Endpoint* then vactosertib

will have shown preliminary efficacy and feasibility to justify further evaluation as an agent to treat anemic patients with Ph-Neg MPNs.

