12.4.2 Analysis of Secondary Endpoints

Clinical response to vactosertib will be assessed using the *Criteria for Clinical Benefit* outlined above as a composite endpoint. Patients achieving any of these criterial will be considered to have achieved clinical benefit. This endpoint will be used to define a preliminary estimate of the potential efficacy of vactosertib in the study population. Complete enrollment to both tiers (37 total) will allow us to confidently identify a *Clinical Benefit* response rate of more than 30%. This estimate has a significance of ≤ 0.1 and a power of 0.8 and is based upon a reported clinical improvement rate of $\leq 10\%$ (almost

entirely due to symptomatic response) in similar patient populations with best available therapy^{34,35}. Reported rates of splenic and/or erythropoietic responses to best available therapy are $\leq 3\%$. The 37 subjects enrolled on this study will allow Splenic Response and Erythropoietic Response rates of at least 20% to be individually tested with a power of 80% and a significance of $< 0.1\%$. If after complete accrual of 37 subjects, more than 11 patients meet criteria for Composite Response, or more than 7 patients meet criteria for Splenic or Erythropoietic Response, vactosertib will be considered to have sufficient efficacy for definitive testing in a randomized study.

The secondary endpoints of erythropoietic (HGB and RBC transfusion), symptomatic, and splenic responses will be directly tested as described in the preceding section. While limited by the small sample size, additional endpoints will be assessed including molecular (MPN driver variant allele frequency), pharmacodynamic (SMAD2/3 phosphorylation in bone marrow and/or blood CD34+ hematopoietic stem and progenitor cells), and histologic (bone marrow cellularity and fibrosis score) responses. The incidence of hematologic toxicities, infections, disease progression, thrombosis events, and the probability of overall and progression free survival, will be monitored. Secondary endpoints will be reported using descriptive statistics but no formal hypothesis testing will be performed.

Other secondary endpoints will be reported using descriptive statistics but no formal hypothesis testing will be performed. The following endpoints will be analyzed:

12.4.2.1 Histologic response defined by any reduction in grade of bone marrow fibrosis by histopathologic assessment at 16 weeks.

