The principal investigator will be primarily responsible for monitoring the safety of the study, adverse events, both serious and non-serious and deaths that occur during study participation by subjects. All adverse events will be monitored until they resolve or are clearly determined to be due to a subject's disease or intercurrent illness(es).

At the completion of Tier 1, all data necessary to evaluate [Criteria for Decision to Proceed to Tier 2](#) section) will be reported to WCM Statistician, WCM DSMB and Medpacto. The Simon Two-stage

Optimum Design is expected to minimize the number of subjects exposed to vactosertib if it is found to be an unsuitable agent for the treatment of anemic patients with Ph-neg MPNs. If 1 or more subjects meets the endpoint then the study will proceed to Tier 2 and another 25 subjects will be enrolled). This decision will be submitted to WCM IRB at the time of continuing review.

After completion of Tier 2, all data necessary to evaluate will be reported to WCM Statistician, WCM DSMB and Medpacto. If four or more subjects meet the Composite Response & Toxicity Endpoint then vactosertib will have shown preliminary efficacy and feasibility to justify further evaluation as an agent to treat anemic patients with Ph-Neg MPNs. This interpretation will be submitted to WCM IRB at the time of continuing review.

Should the Stopping Rules for [Tier 1](#) or for [Tier 2](#) be met, accrual of new subjects will be immediately suspended and the WCM IRB and Medpacto will be notified. The study DSMB will meet to review study data. The DSMB may either recommend permanent closure of the study or may allow protocol revision/amendment and submission to WCM IRB for review. DSMB recommendations will be submitted to Medpacto and WCM IRB.

All protocol amendments and consent form modifications will be made by the Principal Investigator. Medpacto will have the opportunity to review and approve the changes prior to submission of these changes to the local IRB.

[Section 7.9, Criteria for Removal from Study](#), details treatment stopping rules for individual patients.

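### Section 12.1.1 gives two conflicting rules for further development (at least 20% of subjects, and 4 or more of 37), and its under-10% error rates hold only for the second

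*Combined protocol and SAP*

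**What the plan says.** Section 12.1.1 opens with a Simon two-stage optimal design and then gives a condition for going forward: "Further development of vactosertib would be warranted if $\geq 20\%$ of subjects met" the criteria of Section 10.1 without dose-limiting toxicity. After the 1-of-12 continuation rule it gives the error rates: "Using these criteria, there is less than a 10% chance of inappropriately accepting" a drug that is not useful, and "Conversely, there is less than a 10% chance of inappropriately rejecting" one that is.

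Table 4 supplies the design inputs: "Response Probability Indicating Unacceptably Low vactosertib Activity 0.05" and "Response Probability Indicating Substantial vactosertib Activity 0.20". It requires at least 1 responder among 12 to open Tier 2 and at least 4 of a maximum of 37 to advance. The text below repeats this: "After completion of Tier 2, if four or more subjects meet the" composite endpoint of Table 5, further evaluation is justified. Section 15 says the same for reporting to the DSMB and IRB: "If four or more subjects meet the Composite Response & Toxicity Endpoint then vactosertib will have shown preliminary efficacy and feasibility". Table 5 requires clinical benefit for at least 8 weeks and no dose-limiting toxicity.

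Section 12.4.2, on secondary endpoints, sets a bar for a definitive randomized study: "more than 11 patients meet criteria for Composite Response", or more than 7 with splenic or erythropoietic response. It gives its own error rates: significance of at most 0.1 and power 0.8 for a benefit rate above 30% against at most 10%, and 80% power for splenic or erythropoietic rates of 20% against at most 3%. Section 12.4.1 refers the whole primary analysis to Table 4 and Section 12.1.

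**The concern.** As worded, the 20% sentence is a condition on the observed share of subjects. The 4-of-37 rule is a different condition for what is in substance the same decision, and both stand in the one section that defines the primary analysis. The error rates are attached to criteria that include the 20% sentence, so a reader cannot tell which rule they describe.

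The trial is open-label and single-arm, and this is its main go/no-go decision. If the result lands between the two cut-offs, either conclusion can be defended from the text after the data are seen. The endpoints differ too: the 20% sentence omits the 8-week duration that Table 5 requires.

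**Working it through.** **Inputs.** p0 = 0.05, p1 = 0.20, 12 subjects in Tier 1, 37 in total, continue with at least 1 responder, success with at least 4 (all Table 4). The 20% rule comes from the sentence above Table 4.

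**Converting the 20% rule to a count.** 0.20 × 37 = 7.4, so 8 or more of 37 (21.6%). The Table 4 rule is 4/37 = 10.8%. This takes all 37 as the denominator.

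**Formula.** With the continuation rule, success at r or more means a total of at least r and at least one responder in Tier 1. A total of r with none in Tier 1 must come entirely from the 25 Tier 2 subjects, so

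P(success) = P(Bin(37, p) ≥ r) − (1 − p)^12 × P(Bin(25, p) ≥ r).

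**Reproducing the plan's figure, r = 4.**
- p = 0.05: 0.1119 − 0.5404 × 0.0341 = 0.0935. Type I error 9.35%.
- p = 0.20: 0.9550 − 0.0687 × 0.7660 = 0.9024. Power 90.2%, type II error 9.8%.

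Both are below 10%, as stated. A search over two-stage designs for the smallest expected sample size under p0, with both errors at most 10%, returns this same design: continue with at least 1 of 12, success with at least 4 of 37, expected sample size 23.5 at p0. Table 4 is sound.

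**The 20% sentence as a rule, r = 8.**
- p = 0.05: type I error 0.0004, or 0.04%.
- p = 0.20: 0.4670 − 0.0687 × 0.1091 = 0.4595. Power 46.0%, type II error 54%.

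**How often the two rules disagree**, if one responder count serves both (4 to 7 responders):
- true rate 20%: 0.9024 − 0.4595 = 0.443, or 44%;
- true rate 15%: 0.7512 − 0.1776 = 0.574, or 57%.

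**Section 12.4.2 on its own hypotheses** (single-stage binomial, n = 37):

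| Rule | Null rate: alpha | Target rate: power | Stated power |
|---|---|---|---|
| more than 11 (≥12) | 10%: 0.0002 | 30%: 0.43 | 0.8 |
| ≥9 | 10%: 0.009 | 30%: 0.82 | |
| ≥8 | 10%: 0.027 | 30%: 0.91 | |
| ≥7 | 10%: 0.071 | 30%: 0.96 | |
| more than 7 (≥8), splenic or erythropoietic | 3%: 0.00001 | 20%: 0.47 | 0.8 |

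The two cut-offs sit at about the target rates themselves (30% of 37 = 11.1; 20% of 37 = 7.4). A cut-off placed there gives power near one half or less, not 0.8.

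**The case against.** The best defence is that the 20% sentence is only a loose introduction. It opens a Simon design, and Table 4 directly below labels 0.20 as the rate of substantial activity. The cut-off of 4 appears three times, consistently, and is exactly the optimal design for the stated inputs. That probably is the intent, and it is why no design change is needed. It does not remove the conflict: the sentence is phrased as a condition on subjects observed, the error claim follows it, and nothing in the plan says which statement governs.

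The 44% and 57% also assume a common count. The 20% sentence has no 8-week condition, so its count can only equal or exceed the Table 5 count. A trial with 4 to 7 Table 5 responders might therefore still reach 8 under the looser definition. This objection stands as a limit on those two probabilities. It does not affect the 46.0% power.

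A reader might go further and infer that Section 12.4.2 is a third, contradictory threshold, so that any result from 4 to 11 responders gives opposite conclusions. The documents do not support this. That section concerns readiness for a definitive randomized study, whereas the 4-of-37 rule justifies further evaluation; passing one and missing the other is coherent. It states only what would be sufficient, and it has an alternative route through more than 7 splenic or erythropoietic responses. Its paragraph treats meeting any clinical benefit criterion as the composite, which points to Section 10.1 and not to Table 5. Nor are error rates stated for only one rule, since Section 12.4.2 gives its own. What remains there is that the plan does not state the ranking or name the endpoint clearly, and that the stated power does not match the cut-offs.

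**Conclusion.** The point holds for Section 12.1.1. Its two rules differ by a factor of two in the number of responders required, and the under-10% claims are true for 4 or more of 37 and false for 8 or more, where the type II error is 54%. These figures are exact binomial results that assume all 37 subjects are counted and the 1-of-12 rule is applied. The 44% chance of a split result at a true 20% rate also needs the common responder count.

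The most plausible explanation is a wording error, with the target rate written as an observed cut-off. It still has to be corrected because it bears on the primary decision. For Section 12.4.2 the finding is narrower: it is a separate secondary bar whose relation to the primary rule is unstated and whose claimed power of 0.8 is about 0.43 (more than 11) and 0.47 (more than 7).

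**What to change.** 1. **Section 12.1.1.** Replace the 20% sentence with, for example: *A true composite response rate of 20% (null 5%) is considered substantial activity; further evaluation is warranted if at least 4 of 37 subjects (Tiers 1 and 2 combined) meet the Table 5 endpoint.* The error-rate sentence can then stay as it is.
2. **Section 12.4.2, status.** State that its cut-offs are a separate bar for a definitive randomized study, that they do not override the 4-of-37 decision, and which endpoint the composite count uses (apparently Section 10.1 clinical benefit).
3. **Section 12.4.2, numbers.** Either restate the power for the present cut-offs (about 0.43 and 0.47) or change the cut-offs. For 10% against 30%, a rule of 7, 8 or 9 or more of 37 meets alpha of at most 0.1 and power of at least 0.8. For splenic or erythropoietic response (3% against 20%), first settle whether the printed significance of 0.1% means 0.1. If so, 3, 4 or 5 or more of 37 qualifies (at 5: alpha 0.005, power 0.89). If 0.1% is literal, no cut-off reaches 80% power: 6 or more gives alpha 0.0008 and power 0.78.

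The cost is a few sentences. The sample size, the tiers and the Table 4 design stay as they are.

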10.1.1 Symptomatic Response

- Defined by a reduction in MPN-SAS total score by $\geq 50\%$ compared to pretreatment score.

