12.2.2 Composite response/ Toxicity measure

Responding subjects will have met *Criteria for Clinical Benefit* ([section 9.1](#)) for at least 8 weeks. This will ensure that a stable vactosertib dosing schedule can be achieved. Responding subjects will not experience dose limiting toxicity (see *Definition of Dose Limiting Toxicity*). Only subjects meeting all criteria will be considered responders.

Table 5: Composite Response & Toxicity Endpoint

Adequate Response	Meets Criteria for Clinical Benefit
Stable Response	Meets Criteria for Clinical Benefit to vactosertib for \geq 8 weeks
Tolerable	No Dose Limiting Toxicity Experienced

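### Table 4 labels the final cut-off of four as a Tier 2 count, but the stated error rates hold only if it is the total over all 37 subjects

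*Combined protocol and SAP*

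**What the plan says.** Section 12.1.1 and Table 4 set out a Simon optimal two-stage design. The row "Response Probability Indicating Unacceptably Low vactosertib Activity" is set at 0.05, and the rate showing substantial activity at 0.20. Both error probabilities are limited to 0.1; on the first the text says "Using these criteria, there is less than a 10% chance of inappropriately accepting" the drug when it is not useful. Tier 1 has 12 subjects and at least 1 responder is needed to go on. The maximum is 37 subjects.

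The last row of Table 4 reads "Number of Tier 2 Responders to Advance Development" and gives 4 or more. The text below the table says "After completion of Tier 2, if four or more subjects meet the" composite endpoint of Table 5, the drug will have shown "preliminary efficacy and feasibility to justify further evaluation". Section 15 repeats this rule in nearly the same terms. Neither place says whether Tier 1 responders are included in the four.

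A responder for this rule must have clinical benefit lasting at least 8 weeks and no dose-limiting toxicity (DLT). Section 12.2.2 adds: "Only subjects meeting all criteria will be considered responders". Section 12.4.1 refers the analysis of the primary endpoints back to Table 4 and section 12.1.

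**The concern.** The protocol summary and section 12.2 use Tier 2 for the additional 25 subjects. Table 4 has a parallel row for Tier 1 responders, which plainly counts the 12 Tier 1 subjects. Someone applying the table as written would therefore count the four among the 25 Tier 2 subjects only. The prose does not correct this, because *after completion of Tier 2* gives the time of the count and not who is counted.

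This is the primary go/no-go threshold. If the statistician and the data and safety monitoring board (DSMB) read it differently, the same data can give opposite conclusions. A rule applied as labelled would also not have the error rates that the plan states for it.

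**Working it through.** **Inputs** (section 12.1.1, Table 4): n1 = 12; advance if X1 ≥ 1; n2 = 37 − 12 = 25; final cut-off 4; p0 = 0.05; p1 = 0.20; both error limits 0.10. X1 and X2 are independent binomial counts in the two tiers. The DLT stopping rules of section 8 are left out, as they are in Table 4.

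**Reading A: the cut-off is the total of 37.**

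P(accept) = Σ over x = 1 to 12 of P(X1 = x) × P(X2 ≥ 4 − x).

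| Tier 1 responders | Needed in Tier 2 | Product at p = 0.05 | Product at p = 0.20 |
|---|---|---|---|
| 1 | ≥ 3 | 0.3413 × 0.1271 = 0.0434 | 0.2062 × 0.9018 = 0.1859 |
| 2 | ≥ 2 | 0.0988 × 0.3576 = 0.0353 | 0.2835 × 0.9726 = 0.2757 |
| 3 | ≥ 1 | 0.0173 × 0.7226 = 0.0125 | 0.2362 × 0.9962 = 0.2353 |
| 4 or more | 0 | 0.0022 × 1 = 0.0022 | 0.2054 × 1 = 0.2054 |
| **Sum (unrounded terms)** | | **0.0935** | **0.9024** |

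The unrounded sum at p = 0.05 is 0.09347. Type I error is therefore 9.3% and power 90.2%, so both stated limits are met.

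A search over two-stage designs with these inputs, minimising expected sample size under p0, returns exactly this design: stop on 0 of 12, reject on 3 or fewer of 37. The probability of stopping after Tier 1 under p0 is 0.95^12 = 0.540, and the expected size is 12 + (1 − 0.540) × 25 = 23.5.

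**Reading B: the cut-off as labelled, among the 25 Tier 2 subjects.**

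P(accept) = P(X1 ≥ 1) × P(X2 ≥ 4).

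- At p = 0.05: 0.4596 × 0.0341 = 0.0157, a type I error of 1.6%.
- At p = 0.20: 0.9313 × 0.7660 = 0.7134, a power of 71.3% and a type II error of 28.7%.

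The type I limit is still met, but the type II limit of 10% is not.

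**How often the readings disagree.** Any result that passes B has at least 1 + 4 = 5 responders in all, so it also passes A. The probability of disagreement is therefore the difference:

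- At p = 0.20: 0.9024 − 0.7134 = 0.189, or 19% of trials.
- At p = 0.05: 0.0935 − 0.0157 = 0.078, or 8% of trials.

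Example: 3 responders in Tier 1 and 3 in Tier 2 make 6 of 37 (16%). This passes A and fails B.

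**The case against.** The best defence is that no statistician would apply reading B. The final cut-off of a Simon design is cumulative by construction. The row just above gives the maximum of 37, and only the cumulative reading reproduces the stated limits. Section 8.1.1 also says that the Tier 2 stopping rule for toxicity covers everyone enrolled, up to 37, so a rule named after Tier 2 can be cumulative in this protocol. All of this stands, and it shows which reading was intended. It does not make the label right. For the toxicity rule the plan says outright that all subjects count; for the efficacy rule it does not.

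Two stronger readings are tempting, and the documents support neither.

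- *The trial has only 71% power.* That figure belongs to the literal label, not to the design. The design as computed has 90.2%.
- *The type I error claim is wrong because 5% is unsupported.* The claim is correct at the stated 5%. That 9.3% lies close to 10% is normal for a design that minimises expected sample size. The plan does not derive the 5%, but section 12.4.2 gives background rates on best available therapy of up to 3% (splenic and/or erythropoietic response) and up to 10% (clinical improvement, nearly all symptomatic), which bracket it. Table 5 then requires 8 weeks of benefit and no DLT, which lowers the background by an amount that the plan does not state. Nor is the 4-of-37 count the only efficacy bar. Section 12.4.2 sets a higher one for moving to a randomized study: more than 11 of 37 for composite response, or more than 7 of 37 for splenic or erythropoietic response.

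**Conclusion.** The concern holds as a mislabelled decision threshold. Table 4's last row, read as written, does not match the error rates stated beside it, and the text of 12.1.1 and section 15 leaves the count open. The size is 71.3% against 90.2% power, and different decisions in 19% of trials at a true rate of 20%. These figures are exact under binomial sampling, with all 37 subjects counted and no stop for toxicity. They rest on no input from outside the plan.

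The design, the sample size and the cut-off of four are sound. That the 5% is not derived is a missing explanation, not an error. The 9.3% is conditional on a 5% background for the Table 5 composite, and the plan could say so.

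**What to change.** 1. In Table 4, rename the last row *Total responders in Tiers 1 and 2 (of 37) to advance development*, keeping 4 or more.
2. In section 12.1.1 and section 15, write *four or more of the 37 subjects*.
3. Optional: add to 12.1.1 that the type I error of 9.3% is conditional on a 5% background rate for the Table 5 composite, with a sentence on how 5% was chosen given the rates cited in 12.4.2.

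The cost is wording only. There are no extra patients and no change to the design, cut-off or analysis. The clarification should be in place before the Tier 2 count is made, so that it cannot look like a choice made after seeing the data.
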